	APPENDIX C: PATIENT'S MEDICATION DIARY	49
	APPENDIX D: Definitions for Adverse Event Reporting	50
	APPENDIX E: Reporting Timelines	53
	APPENDIX F: Symptom Assessment Form	56

PROTOCOL SUMMARY

Synopsis

Title:	Fostamatinib as a single agent or in combination with ruxolitinib for treatment of patients with myelofibrosis with severe thrombocytopenia
Study Description:	
Our hypothesis is that fostamatinib will be safe, tolerable, and effective in patients with myelofibrosis with severe thrombocytopenia (platelet < 50K/microL) as a single agent and in combination with ruxolitinib. Fostamatinib will improve thrombocytopenia in patients with myelofibrosis (MF) with severe thrombocytopenia (platelet < 50K/microL) and allow them to initiate treatment with ruxolitinib.
 
This study will be executed in two parts (Part A and Part B). For Part A, patients with MF with severe thrombocytopenia will initially receive 12 weeks of single agent fostamatinib (by mouth twice daily) until a sustained platelet count of ≥ 50K/microL is achieved (defined as two separate measurements at least two weeks apart).
 
Patients who achieve a sustained platelet count of ≥ 50K/microL will be eligible to continue on to Part B where they will begin treatment with ruxolitinib (dosed as per standard of care) while continuing to take fostamatinib. Patients who do not achieve a sustained platelet count of ≥ 50K/microL by the end of 12 weeks of treatment may continue on fostamatinib monotherapy if they are receiving benefit for up to an additional 36 weeks of treatment, and may be eligible to continue on to Part B of the study if they achieve a sustained platelet count of ≥ 50K/microL at any point before Cycle 10 Day 1.
 
Patients in Part B will continue treatment with fostamatinib and ruxolitinib for up to an additional 36 weeks (total duration of treatment with fostamatinib monotherapy and fostamatinib and ruxolitinib combination therapy will be 48 weeks).

Objectives:	
Part A:
 
Primary Objective: Evaluate the impact of fostamatinib on platelet counts in patients with myelofibrosis and severe thrombocytopenia (platelets < 50K/microL)
 
Secondary Objectives:
 
 Evaluate the safety and tolerability of single agent fostamatinib in patients with MF and thrombocytopenia Evaluate spleen response to fostamatinib

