	
 3. Evaluate anemia response to fostamatinib 4. Evaluate the impact of fostamatinib on transfusion requirements 5. Evaluate the impact of fostamatinib on MF symptoms 6. Evaluate the ability of fostamatinib treatment to enable initiation with ruxolitinib 7. Evaluate the impact of fostamatinib on marrow fibrosis 
Part B:
 
Primary Objective: Evaluate the safety and tolerability of fostamatinib plus ruxolitinib in patients with MF and thrombocytopenia
 
Secondary Objectives:
 
 1. Evaluate spleen response with the combination of fostamatinib and ruxolitinib 2. Evaluate the impact of fostamatinib and ruxolitinib on symptoms 3. Evaluate the ability of fostamatinib to enable sustained treatment with ruxolitinib 4. Evaluate the impact of fostamatinib and ruxolitinib on marrow fibrosis
Endpoints:	
Part A:
 
Primary Endpoint: Platelet response as defined as an increase in platelet count $\geq 50K/\text{microL}$ with at least one more confirmatory platelet count separated by at least 2 weeks (in the absence of platelet transfusion) within the first 12 weeks of fostamatinib treatment
 
Secondary Endpoints:
 
 1. Platelet response by week 12 and at end of fostamatinib monotherapy treatment 2. Number of patients eligible to initiate therapy with ruxolitinib 3. Adverse events (AEs), serious AEs (SAEs), and laboratory abnormalities on fostamatinib treatment 4. Patients who permanently discontinued fostamatinib due to fostamatinib related AEs 5. Patients who required treatment interruption of fostamatinib due to AEs 6. Patients who were dose escalated who tolerated fostamatinib dose greater than 100 mg BID 7. Patients who achieve 35% or greater reduction in spleen volume as determined by ultrasound at week 12 of fostamatinib treatment and end of fostamatinib monotherapy treatment

	
 8. Mean reduction in spleen volume as determined by ultrasound at week 12 of fostamatinib treatment and end of fostamatinib monotherapy treatment 9. Patients with 50% or greater improvement in Total Symptom Score at week 12 of treatment and end of fostamatinib monotherapy treatment 10. Patients who achieve platelet transfusion independence 11. Patients with anemia who achieve RBC transfusion independence 12. Change in marrow fibrosis by WHO grading

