	
Part B:
 
Primary Endpoint: Incidence, severity, and outcomes of AEs per NCI CTCAE v 5.0, SAEs, AEs of interest (AEIs) and laboratory abnormalities during fostamatinib and ruxolitinib treatment

	
Secondary Endpoints:
 
 1. Patients with 35% or greater reduction in spleen volume as determined by ultrasound after 12 weeks of combination therapy and end of treatment 2. Mean reduction in spleen volume as determined by ultrasound after 12 weeks of combination therapy and end of treatment 3. Patients with a 50% or greater improvement in Total Symptom Score after 12 weeks of combination therapy and at end of treatment 4. Duration of uninterrupted ruxolitinib treatment 5. Change in marrow fibrosis by WHO grading
Study Population:	Twelve adult patients of any race or ethnicity with primary or secondary myelofibrosis with severe thrombocytopenia (platelet count < 50K/microL) with intermediate or high risk disease by IPSS.
Phase:	Pilot Phase II Study
Description of Sites / Facilities Enrolling:	This study will be active at Washington University School of Medicine.
Description of Study Intervention:	Both fostamatinib and ruxolitinib are oral drugs taken twice daily on a continuous basis.
Study Duration:	2 years
Participant Duration:	48 weeks

STUDY SCHEMA

[figure not shown]
Part A:

The starting dose of fostamatinib is 100 mg twice daily (BID). After the first cycle, if no major dose related safety issue is observed and the platelet count is less than 50K/microL, then the fostamatinib dose will be increased to 150 mg BID for the next 2 cycles; otherwise the dose may be continued at 100 mg BID.

Part B:

After 3 cycles of fostamatinib monotherapy, all patients with a sustained platelet count \geq 50K/microL, will continue on the current fostamatinib dose plus ruxolitinib at the recommended dose per standard prescribing guidelines for an additional 9 cycles.

Patients who do not reach platelet count of at least 50K/microL but who achieve clinical benefit per the treating provider may continue on single agent fostamatinib for up to 12 total treatment cycles. If these patients achieve a sustained platelet count of \geq 50K/microL at any point prior to Cycle 10 Day 1, then they may be eligible to enroll in Part B of the study and continue treatment with fostamatinib and ruxolitinib for the remainder of the study.

SCHEDULE OF ACTIVITIES

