5.3 Study Intervention Administration

In Part A of the study, patients will initially receive fostamatinib single agent at a starting dose of 100 mg PO twice daily (BID) for three cycles (12 weeks). Each cycle is 28 days (4 weeks).

Patients who tolerate single agent fostamatinib and achieve a sustained platelet count of $\geq 50,000/\text{microL}$ on at least two separate measurements taken at least two weeks apart at any point before Cycle 10 Day 1 will be eligible to proceed to Part B of the study and initiate treatment with ruxolitinib (starting dose will be determined by platelet count as per package insert).

For patients who do not achieve a sustained platelet count of $\geq 50,000/\text{microL}$ following the first cycle (4 weeks) of fostamatinib 100 mg BID and no AEIs (see Section 5.5) are reported, then the dose of fostamatinib may be increased to 150 mg BID and continued for subsequent cycles. If a platelet count of $\geq 50,000/\text{microL}$ is not achieved after three cycles of fostamatinib, but the patient is achieving clinical benefit, then the patient may continue on fostamatinib monotherapy for up to a total of 12 cycles of treatment and may continue

on to Part B of the study if they achieve a sustained platelet count of $\geq 50,000/\text{microL}$ by Cycle 10 Day 1. If the patient is not achieving clinical benefit or has evidence of disease progression, then the patient will be taken off study.

For Part B of the study, patients will continue on treatment with fostamatinib for up to an additional nine cycles (36 weeks) to complete a total treatment duration of 48 weeks. Ruxolitinib will be initiated in combination with fostamatinib at the start of Part B unless the patient is experiencing progressive MF symptoms and is eligible to initiate ruxolitinib, in which case ruxolitinib may be initiated sooner at the discretion of the PI. If the platelet count decreases to $< 50,000/\text{microL}$ following initiation of ruxolitinib, then the dose of fostamatinib may be increased to 150 mg BID if the patient is on the 100 mg BID dose.

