5.7 Concomitant Therapy and Supportive Care Guidelines

General supportive care measures, including blood and platelet transfusions, antiemetics, administration of granulocyte colony-stimulating growth factors, corticosteroids, and use of antibiotics and antivirals are permitted at the discretion of the treating physician.

It is recommended that nausea, vomiting, diarrhea, or blood pressure elevation be medically managed according to the investigator's discretion.

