10.2.2 Platelet Response

Platelet response is only applicable for patients with a baseline platelet count of less than $50 \times 10^9/L$ for 8 weeks or more, and requires:

- An absolute platelet count of at least $50 \times 10^9/L$ on two separate measurements at least 2 weeks apart

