12.2 Study Design

This is a hypothesis generating limited pilot phase II study evaluating the efficacy and safety of the use of fostamatinib as a single agent and when given in combination with ruxolitinib in patients with intermediate to high risk myelofibrosis. Previous studies with fostamatinib and ruxolitinib monotherapy indicate that toxicity will be low grade and reversible with standard treatment.

This study consists of two parts. For Part A, patients with MF and severe thrombocytopenia will initially receive 12 weeks of single agent fostamatinib and the primary endpoint will be platelet response (defined as platelet count of $\geq 50K/\text{microL}$ as two separate measurements at least two weeks apart) at the end of the 12 week treatment period. Patients who achieve a sustained platelet response will then be eligible to proceed to Part B of the study and begin treatment with ruxolitinib while continuing to take fostamatinib. For Part B, patients will continue treatment with fostamatinib and ruxolitinib for up to an additional 36 weeks and the primary endpoint will be safety as assessed by NCI CTCAE v 5.0. Patients who do not have a sustained platelet response after 12 weeks of treatment but are clinically benefiting from fostamatinib may remain on Part A of the study and be eligible to enroll in Part B if they achieve a sustained platelet response prior to Day 1 Cycle 10 of treatment.

A maximum of 12 patients will be enrolled. A Bayesian sequential monitoring rule will be implemented for safety.

Safety monitoring (Part B): The stopping rule is defined as $\text{Pr}(\theta > \theta_T | \text{data}) > 0.8$, where θ denotes the proportion of AEs of interest as defined in Section 5.5 and θ_T denotes the rate of AEs of interest under the null hypotheses (i.e., 20% AEs of interest). That is, an early termination of the study due to excessive toxicities will be recommended whenever, given the accumulated observed data, there is high chance (i.e., >80% probability) for the “true” AEs of interest rate >20%. The stopping boundaries were obtained using Multc99 version 2.1, a free-download software from M.D. Anderson Cancer Center. Specifically, we assume that the parameter θ follows a prior distribution of beta (0.2, 0.8), i.e., θ with mean = 0.2 but with relatively large variability (non-informative prior). Early stopping will be recommended if we observe 3 patients who experience AEs of interest out of first 5 patients

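### The synopsis excludes transfusion-supported counts from the Part A platelet response, but sections 10.2.2 and 12.2 do not, and no version of the Part B entry rule addresses transfusion

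*Combined protocol and SAP*

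**What the plan says.** The primary platelet response is defined in three places.

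- **Synopsis, Part A primary endpoint.** The 50K/microL threshold, with a confirmatory count at least two weeks apart, "in the absence of platelet transfusion) within the first 12 weeks of fostamatinib treatment". No interval between transfusion and count is given.
- **Section 10.2.2.** An absolute count of at least 50 x 10^9/L "on two separate measurements at least 2 weeks apart". Transfusion is not mentioned.
- **Section 12.2.** The same two-count rule, assessed at the end of 12 weeks. Transfusion is not mentioned.

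Section 2.1 refers the reader to a section 11.2.2 for the response definition. Section 11 has no such subsection. The definition in the measurement section is 10.2.2, which lacks the condition.

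Entry to Part B is stated in four places, none with a transfusion condition:

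- the synopsis study description, where patients with a sustained count "will be eligible to continue on to Part B where they will begin treatment with ruxolitinib";
- the schema, where such patients "will continue on the current fostamatinib dose plus ruxolitinib at the recommended dose per standard prescribing guidelines";
- section 5.3, which requires the threshold "on at least two separate measurements taken at least two weeks apart at any point before Cycle 10 Day 1";
- section 12.2: "Patients who achieve a sustained platelet response will then be eligible to proceed to Part B of the study".

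Section 5.7 permits "General supportive care measures, including blood and platelet transfusions" at the treating physician's discretion. Part A secondary endpoint 2 in the synopsis is "Number of patients eligible to initiate therapy with ruxolitinib", and section 2.1 puts that count in the primary-objective row.

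**The concern.** A platelet count taken soon after a platelet transfusion reflects the transfusion as well as the drug. The trial asks whether fostamatinib raises platelets enough to permit ruxolitinib, and a supported count does not answer that.

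Two things are at stake. First, an analyst working from the body of the protocol would apply 10.2.2 and could report a different primary response rate from one working from the synopsis. Second, the eligibility count could credit fostamatinib with a transfusion effect, and a patient could start ruxolitinib on that basis.

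The situation is foreseeable. Platelet transfusion independence is Part A secondary endpoint 10, section 2.1 expects some patients to have needed transfusions before, and no exclusion criterion removes them. The neighbouring anemia definition (10.2.1) sets a one-month period without red-cell transfusion for its transfusion-independence route. The platelet definition has no counterpart.

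**Working it through.** **1. The plan's own figures.** Section 12.4 gives two binomial probabilities for n = 12. Both reproduce:

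- P(at most 1 response | 20%) = 0.8^12 + 12 x 0.2 x 0.8^11 = 0.0687 + 0.2062 = 0.275 (stated 27%).
- P(at least 2 responses | 40%) = 1 - 0.6^12 - 12 x 0.4 x 0.6^11 = 1 - 0.0022 - 0.0174 = 0.980 (stated 98%).

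The point disputes neither figure, and neither changes if the wording is aligned.

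**2. How one patient would be classified.** Each row assumes two counts of at least 50K, at least two weeks apart, within 12 weeks. I read the synopsis threshold as reaching 50K and its condition as covering both counts.

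| Counts supported by transfusion | Synopsis endpoint | 10.2.2 and 12.2 | Part B entry rule, read literally |
|---|---|---|---|
| Neither | Response | Response | Eligible |
| One | No response | Response | Eligible |
| Both | No response | Response | Eligible |

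If one count was supported, the patient did reach 50K once unaided and only the confirmation is lost. If both were supported, the patient's own count may be below 50K, where section 1.3 says ruxolitinib is not recommended. That takes support at two times at least 14 days apart.

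**3. Size per patient.** With 12 evaluable patients, 1/12 = 8.3 percentage points. Section 12.3 gives hematologic response an exact 95% interval, and platelet response falls under that heading (10.2). The limits are the 2.5% quantile of Beta(x, 13 - x) and the 97.5% quantile of Beta(x + 1, 12 - x):

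- x = 1: 0.2% to 38.5%.
- x = 2: 2.1% to 48.4%.

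Section 12.3 does not name ruxolitinib eligibility among the rates with intervals, so for that count the size is simply 8.3 points per patient.

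**4. Frequency.** The documents give no platelet transfusion rate. As an illustration only, let f be the share of true non-responders counted as responders because of transfusion. The counted rate is p + (1 - p)f. With p = 20%:

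| f (assumed) | Counted rate | Expected extra responders, 12(1 - p)f | P(at most 1 of 12) |
|---|---|---|---|
| 0 | 20% | 0 | 27% |
| 5% | 24% | 0.48 | 18% |
| 10% | 28% | 0.96 | 11% |
| 20% | 36% | 1.92 | 4% |

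**5. How long a transfusion-free window can be.** After Cycle 1, monotherapy CBCs fall on Days 1 and 15, nominally 14 days apart. Day 1 visits may move by 3 days, so the shortest gap is 14 - 3 = 11 days. If w clear days are required, a transfusion on day t rules out counts from day t to day t + w. Two counts 11 days apart cannot both be ruled out if w is at most 10. This assumes that Day 15 is fixed. If the 2-day allowance in note 4 of the schedule, worded for Days 8 and 22, also applied to Day 15, the gap would be 14 - 3 - 2 = 9 days and the limit 8. A 7-day window meets both limits. In Cycle 1, with weekly counts, one transfusion could rule out two counts.

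**6. The Part B cutoff (nominal days).** Cycle 9 Day 1 is 8 x 28 + 1 = day 225, Cycle 9 Day 15 is 8 x 28 + 15 = day 239, and Cycle 10 Day 1 is 9 x 28 + 1 = day 253. A patient transfused on day 239 has no later scheduled count before the cutoff. With w = 7, days 240-246 are clear and a repeat is possible on days 247-252, at least 247 - 225 = 22 days after the Cycle 9 Day 1 count.

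**The case against.** The strongest reply is that the plan already means one thing. Section 12.2 opens Part B on a sustained platelet response, and the synopsis defines platelet response with the transfusion condition. On that reading only the drafting is loose. This has force as to intent, but 12.2 also writes out its own definition without the condition, so the text does not settle the matter.

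A reader might infer that the entry rule contradicts the synopsis. It does not. The synopsis attaches the condition to the primary endpoint, and its own entry rule omits it, as do the schema, 5.3 and 12.2. The conflict is between the response definitions. For entry there is a gap.

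A reader might also infer that nothing protects the patient until ruxolitinib has started. That is not supported either. Section 5.3.2 sets the starting dose from the platelet count, with 5 mg BID at 50-100K and no dose listed below 50K, and a CBC is scheduled on Day 1 of each cycle. After the start come weekly CBCs in the first combination cycle, dose modification (6.1, 6.2), PI discretion (6.0) and the stopping rule for adverse events of interest (5.4). These reduce the risk, but none excludes a transfused count.

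It is also fair that platelet transfusion independence is reported separately and transfusions are recorded continuously, so support could be seen beside the eligibility count. That helps interpretation but does not say which response rate is primary. Analyses are descriptive, and no go/no-go threshold rests on either count.

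**Conclusion.** The point holds as a conflict between two stated definitions of the Part A primary response, together with an entry rule that does not address transfusion. Each patient affected moves the response rate or the eligibility proportion by 8.3 points, assuming 12 evaluable patients. Within 12 weeks the body definitions can only give a rate equal to or higher than the synopsis definition, so the discrepancy runs in the drug's favour.

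The documents do not show that any patient will be misclassified or how often. The values of f above are assumptions. Nor do they support the inference that patients would routinely start ruxolitinib with an unsupported count below 50K, because that needs support at both counts. The point deserves correction because it touches the primary endpoint and the written platelet criterion for a second drug, and because correction is cheap. It does not undermine the design or the figures in section 12.4.

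**What to change.** Require that each qualifying count be free of platelet transfusion for a fixed number of days beforehand. Seven days is an assumed example for the sponsor to confirm. The window should not exceed 10 days, so that after Cycle 1 one transfusion disqualifies at most one scheduled count (8 days if Day 15 visits may also move by 2).

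- Put the condition and window in 10.2.2 and 12.2, and in the entry rule in the synopsis, schema and 5.3. Add the window to the synopsis primary endpoint, and correct the cross-reference in 2.1.
- Keep the time limits separate: the first 12 weeks for the primary endpoint, before Cycle 10 Day 1 for entry.
- Derive the response and eligibility counts from Transfusion Form and CBC Form dates.
- Allow an unscheduled repeat CBC when a count near the Cycle 10 Day 1 cutoff is disqualified.

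The cost is wording, one derivation from forms already in the data schedule, and an occasional extra CBC. Both counts may be slightly lower, and a transfused patient may wait about two weeks longer to enter Part B. Without the repeat CBC, a patient who needs the Cycle 9 Day 15 count but was transfused would miss entry for scheduling reasons alone.

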5.3.1 Dosing of Fostamatinib

Fostamatinib is an oral drug which will be given at a starting dose of 100 mg BID each day of a 28-day cycle. The dose of fostamatinib can be increased to 150 mg BID after Cycle 1 if the platelet count remains $< 50,000/\text{microL}$. Fostamatinib should be taken at approximately the same times each day, with or without food. In case of a missed dose, patients should be instructed to resume dosing at the next scheduled dose. Patients will be instructed to bring all unused drug and their medication diary (Appendix B) to each study visit for assessment of compliance.

5.3.2 Dosing of Ruxolitinib

Ruxolitinib is an oral drug which will be taken twice daily each day of a 28-day cycle. The starting dose of ruxolitinib given will depend on the patient's baseline platelet count. If platelets are $> 200,000/\text{microL}$, patients should take 20 mg BID. If platelets are between 100,000/ microL and 200,000/ microL , patients should take 15 mg BID. If platelets are between 50,000/ microL and 100,000/ microL , patients should take 5 mg BID. Ruxolitinib should be taken at approximately the same times each day, with or without food. In case of a missed dose, patients should be instructed to resume dosing at the next scheduled dose. Patients will be instructed to bring their medication diary (Appendix C) to each study visit for assessment of compliance.

5.4 Toxicity Monitoring (Stopping Rules)

A Bayesian sequential monitoring rule will be used to protect patients from excessive toxicities (see Section 12.2 for technique details), and the table below shows the boundaries of early stopping rule. That is, an early stopping of the study due to excessive toxicities will be recommended if we observe 3 patients who experienced AEs of interest (as defined in Section 5.5) out of the first 5 patients or 4 patients who experience AEs of interest out of first 9 patients.

# Patients treated	1	2	3	4	5	6	7	8	9	10	11	12
Stop if the # AEIs \geq	N/A	N/A	N/A	N/A	3	3	3	3	4	4	4	4

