2.2 Part B Objectives and Endpoints

Objectives	Endpoints	Justification for Endpoints
Primary		
To evaluate the safety and tolerability of the combination of fostamatinib and ruxolitinib in MF patients	Incidence, severity, frequency, and outcomes of AEs and SAEs as defined by CTCAE v5.0 criteria and AEs of interest (AEIs) as defined in section 5.5	The safety of this combination therapy in MF patients is not known.
Secondary		
To evaluate the spleen response in patients with MF receiving fostamatinib in combination with ruxolitinib	Spleen response as detailed in Section 11.4 after 12 weeks of combination therapy, mean reduction in spleen volume as determined by ultrasound after 12 weeks of combination therapy and at the end of treatment	The efficacy of fostamatinib in combination with a JAK inhibitor on reducing spleen size in patients with MF is unknown
To evaluate the impact of fostamatinib in combination with ruxolitinib on constitutional symptoms in patients with MF	Constitutional symptoms as detailed in Section 11.3 after 12 weeks of combination therapy and at the end of treatment	The efficacy of fostamatinib in combination with a JAK inhibitor on symptoms in MF is unknown
Evaluate the ability of fostamatinib to enable sustained treatment with ruxolitinib	Duration of uninterrupted JAK inhibitor (ruxolitinib) therapy	The ability of fostamatinib to maintain an adequate platelet count for patients

		to remain on JAK inhibitor therapy is unknown
To evaluate the impact of fostamatinib and ruxolitinib on marrow fibrosis	Change in marrow fibrosis per WHO grading on bone marrow biopsy performed at the end of fostamatinib and ruxolitinib therapy	The impact of fostamatinib and ruxolitinib combination therapy on marrow fibrosis is unknown

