5.5 Adverse Events of Interest (AEIs)

Adverse events of interest (AEIs) are defined as clinically relevant grade 3 or 4 adverse events considered possibly, probably, or definitely related to either fostamatinib or ruxolitinib as defined by CTCAE v5.0 criteria and are not related to the underlying disease.

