12.4 Sample Size and Study Power

A total of 12 patients will be enrolled. As a pilot phase II study for hypothesis generating, formal power calculations to determine sample size were not performed. Based on simulation studies regarding the sample size for translational studies, however, Piantadosi recommends that a sample size of 10 to 20 patients be adequate to provide preliminary information [33]. For efficacy, for example, the probability of observing at most 1 platelet response out of 12 patients is 27% given that the true rate is 20%. However, the probability of observing at least 2 platelet responses is 98% given that the true is 40%. For safety, if the “true” AEs of interest rate is 20% or higher, there will be more than 93% chance to observe at least 1 patient with AE of interest out of 12 patients. Conversely, there is less than 2% chance to observe 3 or more patients with AE of interests if the “true” rate is 5% or less.

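### Sections 5.4 and 12.2 disagree on whom the toxicity rule monitors, and on neither reading do the stated 4% and 76% chances to stop describe the combination

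*Combined protocol and SAP*

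**What the plan says.** Section 5.4 gives one rule for the whole study: "an early stopping of the study due to excessive toxicities will be recommended if we observe 3 patients who experienced AEs of interest" among the first 5, or "4 patients who experience AEs of interest out of first 9 patients". Its table is indexed by "Patients treated", from 1 to 12, with N/A at 1 to 4, a limit of 3 at 5 to 8 and a limit of 4 at 9 to 12. There is no split by part. For the method it refers the reader onward: "see Section 12.2 for technique details".

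Section 12.2 prints the same table but opens differently: "Safety monitoring (Part B): The stopping rule is defined as" a posterior probability above 0.8 that the AEI rate exceeds 20%, with a beta(0.2, 0.8) prior. It states a 4% chance to stop at a true AEI rate of 10% and 76% at 40%.

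Section 5.5 defines AEIs as clinically relevant grade 3 or 4 events "considered possibly, probably, or definitely related to either fostamatinib or ruxolitinib". Section 5.6 makes every treated patient evaluable for toxicity. Only patients with a sustained platelet response go on to Part B (5.3, 12.2). Section 2.2 makes combination safety the Part B primary objective and gives the reason: "The safety of this combination therapy in MF patients is not known".

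**The concern.** Part B is a subset of the 12 patients and is likely to be small. A rule that counts all treated patients and a rule that counts Part B patients behave very differently, and the plan does not say which is meant. The stated 4% and 76% are the only description of how well patients are protected, and a reader of 12.2 will take them as applying to the combination. If they do not, the monitoring committee and the IRB are relying on a figure that does not describe the phase whose safety is the primary endpoint. The study team would also lack an agreed denominator when combination AEIs appear.

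**Working it through.** **Inputs.** From 12.2: prior beta(0.2, 0.8), AEI limit 20%, posterior threshold 0.8, and at most 12 patients. From the tables: N/A at n = 1–4, 3 at n = 5–8, 4 at n = 9–12. From 12.4: illustrative platelet response rates of 20% and 40% (for instance "the probability of observing at least 2 platelet responses is 98% given that the true is 40"%). Assumed here: every responder enters Part B, and monotherapy AEI rates are 5%, 10% or 20%, because the plan gives none.

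**1. Reproduce the boundaries.** With k AEI patients among n, the criterion is 1 − F(0.2; 0.2 + k, 0.8 + n − k) > 0.8, where F is the beta distribution function.

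- 2/5 = 0.797 (continue) and 3/5 = 0.960 (stop)
- 3/8 = 0.838 (stop) and 3/9 = 0.785 (continue)
- 4/9 = 0.934 and 4/12 = 0.829 (both stop)

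The limits at n = 5–12 reproduce exactly.

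**2. Reproduce the 4% and 76%.** An exact patient-by-patient binomial recursion over the table, run to 12 monitored patients, gives 4.3% at a 10% AEI rate and 76.4% at 40% when a crossing at n = 12 is not counted as early stopping. Counting it gives 4.7% and 81.1%. The stated figures therefore assume a run to 12 monitored patients with one common AEI rate.

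**3. If all treated patients are counted.** Suppose AEIs occur in 3 of 3 combination patients and in nobody else.

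| Patients treated | 8 | 9 | 10 | 11 | 12 |
|---|---|---|---|---|---|
| Posterior for 3 AEIs | 0.838 | 0.785 | 0.728 | 0.670 | 0.613 |
| Rule | stop | continue | continue | continue | continue |

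The same criterion applied to those three patients alone gives 3/3 = 0.996. One AEI in any other patient makes four and stops the study. With nine others, that chance is 1 − (1 − p)^9:

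- p = 5%: 1 − 0.630 = 37%
- p = 10%: 1 − 0.387 = 61%
- p = 20%: 1 − 0.134 = 87%

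**4. If only Part B patients are counted.** The table shows N/A at n = 1–4, so 3 of 3 again triggers nothing. The plan's own criterion is nevertheless met there: 1/1 = 0.884, 2/2 = 0.979, 2/3 = 0.932, 2/4 = 0.869, 3/3 = 0.996.

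Expected Part B size is 12 × 0.20 = 2.4 or 12 × 0.40 = 4.8. With N_B ~ Binomial(12, r), P(N_B ≥ 5) is 7% at r = 20% and 56% at r = 40%.

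At a 40% AEI rate, the table's chance to stop is 0 for N_B ≤ 4, then:

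| Part B size | 5 | 6 | 7 | 8 | 9 | 10 | 11 |
|---|---|---|---|---|---|---|---|
| Chance to stop | 0.317 | 0.456 | 0.580 | 0.685 | 0.685 | 0.718 | 0.764 |
| P(size), r = 20% | 0.0532 | 0.0155 | 0.0033 | 0.0005 | 0.0001 | <0.0001 | <0.0001 |
| P(size), r = 40% | 0.2270 | 0.1766 | 0.1009 | 0.0420 | 0.0125 | 0.0025 | 0.0003 |

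Multiplying and summing (size 12 adds a negligible amount):

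- r = 20%: 0.0169 + 0.0071 + 0.0019 + 0.0004 ≈ 0.026, about 3%
- r = 40%: 0.0721 + 0.0805 + 0.0585 + 0.0288 + 0.0085 + 0.0018 + 0.0002 ≈ 0.250, about 25%

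The stated figure is 76%.

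**The case against.** **Whole-study monitoring is coherent.** Section 2.1 says that fostamatinib's safety in MF is itself unknown, and AEIs cover either drug, so counting every treated patient is a defensible safeguard. This stands, and it rules out describing the rule as diluting a new combination with a well-understood monotherapy. It does not make 76% a statement about the combination, because that figure needs a 40% AEI rate in all 12 patients.

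**The N/A entries may be deliberate.** A minimum number of patients before the first look is ordinary practice; without one, the criterion would stop at 1 of 1. That is reasonable, but the plan neither states such a minimum nor reconciles it with a Part B that may never reach five patients.

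**Other oversight exists.** Section 11.0 requires ongoing review of serious toxicity and semi-annual reports to the QASMC that include stopping-rule data. This limits the harm but is not a numerical trigger.

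**Two stronger readings are tempting.** A reader might infer that pooling is settled, so that the combination has no trigger of its own and 3 of 3 could never stop the study. The documents do not support that. Section 12.2 assigns the rule to Part B, and even under pooling the result needs no AEI in any other patient and a third AEI patient arising after the ninth patient has been treated.

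A reader might also infer that a combination-only count must be added. Its benefit depends on assumptions. I simulated one patient per month, Part B entry at 3 months, AEIs within 3 months of starting a phase, a 60% combination AEI rate and 20% response. Adding such a count from the second combination patient raised stopping from 14% to 43% at a 5% monotherapy AEI rate, but only from about 54% to 65% at 20%. Separating the denominator while keeping the N/A entries moved it only from 13% to 14% at the 5% rate, so much of the gain comes from earlier looks. At a 20% combination AEI rate and 40% response (monotherapy 5%), the added count raised stopping from 6% to 17%.

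**Conclusion.** The point stands as a contradiction over the monitored set and as operating characteristics that do not fit the combination. The boundaries at n = 5–12 and the 4% and 76% are computed correctly, but for 12 monitored patients. A responder-only Part B gets there only if all 12 patients respond.

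Counting all treated patients, three AEIs in three combination patients can leave the study open, subject to the conditions above. Counting Part B only, the chance to stop at a 40% AEI rate is about 3% or 25%. These sizes rest on the illustrative response rates in 12.4 and on every responder entering Part B. The monotherapy AEI rates are assumptions. The plan is not shown to be unsafe, and no particular extra stopping rule follows from this.

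**What to change.** - State the monitored set, the denominator and the AEI counting window once, in the same terms, in 5.4, 12.2 and both tables. Say whether the first 5 and first 9 are treated patients or Part B patients, and whether AEIs that start before ruxolitinib count.
- Reconcile the N/A entries at n = 1–4 with the stated posterior criterion, for example by stating the minimum number of patients if one is intended.
- Replace the single 4% and 76% statement with the chance to stop for the combination at realistic Part B sizes, for example 2 to 5 patients, over a range of assumed monotherapy AEI rates. Say whether a crossing at the last patient counts.

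Whether to add a combination-only count, and what action would follow a crossing, is for the sponsor and the QASMC to decide. The cost is a short edit to two sections and a simulation rerun, with no new data or patients. The downside is a less favourable stated figure.
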